3 OBJECTIVES AND ENDPOINTS

OBJECTIVES	ENDPOINTS	JUSTIFICATION FOR ENDPOINTS
Primary		
Identify the causal effect of income instability on psychological health, biomarkers of stress, and physical health.	Depression (PHQ) Anxiety (GAD) Stress (cortisol) Blood pressure Dietary diversity and sufficiency	Depression, Anxiety, and Stress are three key elements of mental health that are likely to be impacted by income volatility and uncertainty. Blood pressure is a potential downstream consequence of such stress. Dietary diversity and sufficiency are key proxies for the likely long-term impacts of instability and uncertainty on physical health via nutrition.

	OBJECTIVES	ENDPOINTS	JUSTIFICATION FOR ENDPOINTS
Secondary			
1)	Decompose the effects identified above into the effects of predictable and unpredictable income	The endpoints for (1) are the same as the primary objective. The analysis varies by looking at the underlying drivers rather than the overall impacts.	Endpoints for (1) are outcomes. Endpoints for (2) are mediators and moderators.
	instability and compare them to the impact of increasing the average level of income.	Additionally, we will examine other elements of mental health and well-being including stress (self-reported),	
2)	Investigate the channels through which effects on health occur, including both economic and behavioral channels	worry (Penn State), Subjective well-being (Cantril and Deiner's), absolute weight, and relative weight change (in kg and percent change.	
	and estimate the impact of key moderating factors.	Endpoints for (2) include measures of income and consumption dynamics (e.g., savings/debt, transfers, consumption, and additional labor supply) and key demographics (e.g. age, gender, baseline mental health)	

4 STUDY DESIGN

4.1 OVERALL DESIGN

The study will consist of a 4- arm phase-3 randomized controlled trial to avoid concerns around the measurement and endogeneity of income streams and participants knowledge of those income streams. We hypothesize that the impact of the treatments on our primary endpoints will be positive overall (due to the increased work and income), but that the Stable Income will have the largest treatment effects, the Predictable Volatility arm the next largest, and the Unpredictable Instability arm the least (though still positive relative to the control).

The randomization will be at the individual level, stratified by village. Participants will be randomized among 4 arms:

1) The Control Arm: The Control arm will not be hired by the cash-for-work program but will be surveyed;

2) The Stable Income Arm: The Stable Income arm will work the same number of days and earn the same amount every two-week period;

3) The Predictable Instability Arm: The work days and earnings of the Predictable Instability arm will vary over time. In three periods, the participant will work more days and will earn more. In the remaining three periods, she will work fewer days and will earn less. Crucially, she will be able to predict all swings in her study earnings in the future—i.e., she will know her work days and earnings in each future two-week period.

4) The Unpredictable Instability Arm: The work days and earnings of the Unpredictable Instability arm will vary unpredictably over time. In any given two-week period, there will be a 50% chance that she works more days and earns more and a 50% chance that she works fewer days and earns less.

Randomization will be done using statistical software for the treatment assignments and a process of drawing sealed envelopes for the period-by-period realizations in the Unpredictable Instability arm (to increase trust in the randomization process). The Control, Stable, Predictable Volatility arms will each have 400 participants. The Unpredictable Instability arm is overweighted with 1,067 participants, as the analysis of this arm will be disaggregated depending on the draws realized by each participant. The participant will learn of their study arm assignment after consent and the baseline survey, but prior to the beginning of the first 2-week period. The PIs and associated staff under their direction will generate the randomization code and output, with the exception of the period-by-period draws for the Unpredictable Instability participants which will occur in the field.

Unpredictable Instability participants will realize their draw for the next period in the five days between the time when the work for the prior period is completed and the work for the next period begins. This randomization is assured to be truly random via the following procedure:

- The field officer arrives at the participant's house with two sealed envelopes. One contains a "high" draw and the other a "low" draw for the period, as indicated by a work calendar. Both have the participant's ID number on the outside of the reverse (sealed) side of the envelope.
- The participant selects and opens one envelope
- The field officer photographs the calendar from the open envelope in the same frame as the sealed envelope with the same participant ID. This ensures that we can verify which envelope was opened first, and hence the draw of the participant for that period.
- The participant then opens the second envelope to verify that it held the other type of calendar/draw.

While we do not anticipate having randomization errors, should they occur, we will drop those participants from the study.

Each participant will be enrolled for 6 2-week periods. In addition, they will respond to an eligibility survey roughly 2-4 weeks prior to enrollment and complete a follow-up survey 1 month following the end of the active study period.

All participants will be enrolled from a single site surrounding Tamale, Ghana.

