Effect of Ex-Ante Income Uncertainty. We will estimate *ex-ante* income uncertainty by comparing Unpredictable Instability and Predictable Instability participants with *identical earnings profiles over time.* E.g., we will compare the Unpredictable Instability participants to the Predictable Instability participants. They had identical profiles over the first 4 periods. But, the Predictable Instability participant knew these income swings in advance while the Unpredictable Instability participant did not. The comparison is internally valid because the earnings profile for the Unpredictable Instability participant is randomly determined. To compensate for using a subsample of the arm, more individuals will be assigned to it.

Effect of Income	Table 4: Group Comparisons and the Effects They Estimate			
estimate the effect of	Comparison of	Estimates Effect of		
income realizations	Stable Income to Control	Level of Income		
(what actually happened) by	Predictable Instability to Stable Income	Predictable Instability		
comparing	Unpredictable Instability to Predictable Instability	Unpredictable Instability		
Unpredictable Instability	Unpredictable Instability and Predictable Instability with Identical Earnings Profiles over Time	Ex-Ante Income Uncertainty		
participants who by chance end up with	Unpredictable Instability w/ Diff. Income Realizations	Ex-Post Income Realizations		

different income realizations.

Justification of the Control: For our study we will randomly select individuals from those determined to be eligible to serve as an internal control group for comparison as there may be significant time trends in this population given the progression through the lean season. These individuals will be surveyed following the same timeline as all other participants, but not participate in the work program. Given that our sample density is less than five percent in any selected village, we do not anticipate spillovers from randomly sampled individuals in treatment arms to or from individuals in the control arm.

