6.4 STUDY INTERVENTION/EXPERIMENTAL MANIPULATION ADHERENCE

The participant's adherence to study procedures among treated participants will be tracked using the same datasets used to track fidelity to the intervention because this dataset captures not only that the material was provided to the participant, but also what work the participant has completed using that material. This dataset, generated from the electronic surveying records, allows us to track that engagement with the work provided is high and consistent across all arms of the study. Data is uploaded and a monitoring script is run daily.

However, participants will be retained in the study (and all corresponding survey activities) regardless of their engagement with the work provided as long as they wish to do so.

Adherence to surveys will also be tracked via the electronic surveying software used. We will generate bi-weekly reports (the same frequency as the surveying) on survey engagement across study arms.

We will work to survey all participants originally recruited, including any who drop out of the program, and expect a high tracking rate because: (i) the endline will be conducted only three months post-baseline; (ii) we will stay in frequent contact through the phone surveys; and (iii) IPA Ghana has a strong follow-up protocol and rates (over 94% (Amadu et al. 2018; Wolf et al. 2018)). We will estimate bounds if response rates vary across arms. Given IPAs performance on previous lean season surveys (when respondents typically have time), we anticipate 5% attrition across all arms.

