9.2 SAMPLE SIZE DETERMINATION

Given IPAs' performance on similar previous surveys during the lean season (when respondents are relatively available), we assume a uniform 5% attrition across all arms.

We will recruit 2,267 participants. 1,067 will be assigned to the Unpredictable Instability arm and 400 to each one of the other three study arms. About 37.5% of the Unpredictable Instability arm (i.e., 400 individuals) are expected to have Neutral 4-period schedules, such that the estimation of the effect of ex-ante income uncertainty corresponds to a randomized controlled trial with a sample size of 760 (95% of 800) equally split between "treatment" and "control". For a two-tailed test with 0.05 significance level and 0.8 power, the minimum detectable effect (MDE) is 0.2 of a standard deviation (SD) for each primary outcome (calculations done in Stata). These effect sizes are consistent with those found in the literature on the effects of cash transfers in low-income settings (e.g., Haushofer & Shapiro, 2016 & 2018; McIntosh & Zeitlin, 2020). Similarly, the MDE for the effect of predictable income volatility is also 0.2 SD. The estimation of the effect of income risk, which corresponds to RCT where 72.7% of the 1,394 (95% of 1,467) participants are assigned to the treatment condition, has an MDE of 0.17 SD. The estimation of the effect of income realizations has an MDE of 0.19 SD if those with unlucky and lucky schedules are grouped together and of 0.23 SD if they are each compared separately to those with Neutral schedules. For panel data analyses, standard errors will be clustered at the individual level (the unit of randomization) (Abadie et al. 2017). These are conservative estimates that consider data from the follow-up survey only; they ignore that we will have baseline measures of all outcomes of interest, which should substantially reduce MDEs, and that we will have repeated measures of most outcomes. In addition to an index of mental health, given the rapid evolution of multiple hypothesis testing techniques, will we use state of the art techniques to adjust for multiple hypothesis testing.

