9.3 POPULATIONS FOR ANALYSES

The primary analysis will be intention-to-treat (all randomized participants).

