9.4.2 ANALYSIS OF THE PRIMARY ENDPOINT(S)

We will use the standardized scoring approaches to all mental health outcomes, including any reversals of scale items as needed. These measures are repeated as described in the timelines previously.

ANCOVA regressions, as outlined in section 9.4.1 above, will be run to analyze the differences between experimental arms. Standard errors will be clustered by individual in all panel regressions. Results will be presented in a regression table with point estimates and standard errors. The regressions will be intention to treat (ITT) with all available data. Data will be cleaned to winsorize outliers, but no imputation will be conducted. If attrition is imbalanced, bounding exercises will be conducted. Given the rapid evolution of multiple hypothesis testing techniques, will we use state of the art techniques to adjust for multiple hypothesis testing.

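### Section 4.1 drops participants with undefined randomization errors from the study, contradicting the intention-to-treat population of all randomized participants in Section 9.3

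*Combined protocol and SAP*

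**What the plan says.** Section 4.1 assigns arms once by software. For the Unpredictable Instability arm it adds a period-by-period field draw between two sealed envelopes, one high and one low. A photograph shows the opened calendar beside the still-sealed second envelope; after that, "The participant then opens the second envelope to verify that it held the other type of calendar/draw". The exclusion rule follows directly: "While we do not anticipate having randomization errors, should they occur, we will drop those participants from the study". The section does not say what counts as an error, who decides, whether the woman's surveys stop, or whether her completed rounds are kept.

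Section 9.3 says: "The primary analysis will be intention-to-treat (all randomized participants", with no exception. Section 9.4.1 analyses by assignment whatever the compliance, and Section 9.4.2 uses all available data without imputation. On follow-up, Section 6.4 says: "We will work to survey all participants originally recruited, including any who drop out of the program".

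Bounding is planned in two places. Section 6.4: "We will estimate bounds if response rates vary across arms". Section 9.4.2: "If attrition is imbalanced, bounding exercises will be conducted".

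Section 4.2 defends the comparison of Unpredictable and Predictable participants with the same earnings profile in these terms: "The comparison is internally valid because the earnings profile for the Unpredictable Instability participant is randomly determined". Section 9.2 sizes that comparison: "About 37.5% of the Unpredictable Instability arm (i.e., 400 individuals) are expected to have Neutral 4-period schedules".

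**The concern.** A participant with a randomization error has, by definition, been randomized. Dropping her follows Section 4.1 and breaks Section 9.3; keeping her does the reverse. The plan gives the analyst both instructions and no way to choose between them.

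Three features make this more than a slip of wording. The term is undefined and participants are not blinded (Section 6.3), so the exclusion is left to judgement after assignment is known. The rule covers all four arms, but repeated field draws happen in only one, so most opportunities for error lie there. And neither bounding provision says whether women dropped under Section 4.1 count as attrition, or whether draw groups within the Unpredictable arm are covered.

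At stake is the protection that randomization gives to every contrast involving the Unpredictable arm, if women leave it because of something that happened at a draw.

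**Working it through.** **1. The texts side by side.** Section 9.3 includes all randomized participants; Section 4.1 removes some of them. Section 7.2 comes nearest to a reconciliation, but it only allows replacement of randomized women who did not receive their assignment information or the intervention. It does not reach an error found at a later draw. No other section resolves the conflict.

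**2. The plan's own precision (Section 9.2).** Inputs: two-sided 0.05, 80% power, 5% attrition, 1,067 Unpredictable and 400 in each other arm. Formula: MDE = (1.96 + 0.84) × √(1/n1 + 1/n2), in SD units.
- Schedule-matched contrast: 0.375 × 1,067 = 400 Neutral women, and 95% of 400 is 380. With 380 v 380, MDE = 0.203 SD (stated: 0.2).
- Whole-arm contrast: 95% of 1,467 = 1,394, or about 380 v 1,014. MDE = 0.168 SD (stated: 0.17).

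Both reproduce, so the sample size is not in question.

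**3. Number of draws.** There are six periods. Section 4.1 places each draw between the end of work in one period and the start of the next, which leaves unclear how period 1 is drawn. The count is therefore five or six per woman: 1,067 × 5 = 5,335 or 1,067 × 6 = 6,402 in all.

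**4. Share dropped (illustration).** The documents give no error rate, so the rate e per draw is assumed, as is independence between draws. Share dropped by endline = 1 − (1 − e)^k.

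| Assumed e | k = 5 | k = 6 | Women of 1,067 (k = 6) |
|---|---|---|---|
| 0.1% | 0.5% | 0.6% | 6 |
| 0.5% | 2.5% | 3.0% | 32 |
| 1% | 4.9% | 5.9% | 62 |
| 2% | 9.6% | 11.4% | 122 |

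The other arms lose nobody by this route. All six draws count for the Neutral group too: its schedule is defined over four periods, but a woman dropped at draw 5 or 6 is also missing at endline. At 2%, 11.4% of 400 is about 46 women.

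**5. Precision.** At 2% and six draws, the whole-arm MDE goes from 0.168 to 0.172 SD and the schedule-matched MDE from 0.203 to 0.210 SD. Loss of power is minor.

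**6. Selection.** Shift in the group mean = share dropped × difference between dropped and retained women. The difference is assumed to be 0.2 to 0.4 SD.
- Low end: 0.006 × 0.2 = 0.001 SD.
- High end: 0.114 × 0.4 = 0.046 SD.

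The same range applies to the whole-arm mean and to the schedule-matched group mean, if errors strike all draws alike. The high end is 0.046/0.17 = 27% of the whole-arm MDE and 0.046/0.2 = 23% of the schedule-matched MDE. These figures are unadjusted and apply at endline. If completed rounds were kept, the effect on the panel estimate would be smaller.

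**The case against.** The best case for the sponsor is that nothing may happen. The protocol expects no errors, and labelled envelopes, the photograph and the second-envelope check exist to prevent or catch them. A packing mistake need not relate to anyone's outcome. This stands: every rate and difference in the illustration is assumed, and it does not show a bias.

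Second, an exclusion can be defended for some contrasts. If the pair was not one high and one low, the resulting schedule is not verified as random, and keeping the woman in a schedule-matched comparison also weakens the ground that Section 4.2 claims. This stands too, but it supports reporting those contrasts both ways. It does not support removing her from the study or from the arm-level analysis, where her assignment remains valid.

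A reader might infer three stronger things.
- That the planned bounds cannot deal with selection between draw groups. Section 6.4 is tied to differences across arms, but the trigger in Section 9.4.2 is imbalanced attrition, with no limit to arms. The text is silent, not exclusive.
- That Section 6.4 flatly contradicts the drop rule. Its sentence describes a follow-up effort aimed mainly at women who leave the work program; the two sit uneasily together, but the real contradiction is with Section 9.3.
- That errors would cluster after low draws and distort the comparison of income realizations. No text suggests such a pattern.

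Finally, Section 10.1.10 already requires deviations to be recorded, and a manual of procedures not seen here may log the second-envelope check.

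**Conclusion.** The point holds as a contradiction in the analysis population, and it should be corrected. That part rests on the text alone and is secure: the exclusion in Section 4.1 cannot be followed together with Sections 9.3, 9.4.1 and 9.4.2, and its trigger is undefined.

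That exclusions would fall mostly in the Unpredictable arm is a probable consequence of where the draws take place. The numerical effect is unknown and probably small. Even the top of the illustrated range, which needs a 2% error rate at every one of six draws and a 0.4 SD difference, stays well below the effects the trial is sized to detect. The documents do not support a claim that the results would be materially biased.

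**What to change.** Delete the drop sentence in Section 4.1 and replace it with the following, carrying the analysis wording into the pre-analysis plan that Section 9.4.1 promises before the main study.

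- Define a randomization error, separating arm-assignment errors from period-draw errors.
- Keep every randomized woman in the surveys, unless she withdraws, and in the ITT analysis under her assigned arm. Exclude flagged cases only in a sensitivity analysis.
- Where the envelope pair was valid, code the draw as the first-opened envelope in the photograph.
- Where the pair was invalid or the draw cannot be verified, keep the woman in the arm-level contrasts and report the schedule-matched and realization contrasts with and without her.
- Record the result of the second-envelope check at every draw. The photograph is taken while that envelope is sealed, so it cannot reveal an invalid pair.
- Report error counts by arm and by draw.

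Sample size and visits do not change. The cost is protocol and analysis-plan wording, one recorded item per draw if it is not already logged, and a small amount of adjudication, coding and extra analysis. The statistical downside is slight dilution from the few women with errors who stay in.

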4.2 SCIENTIFIC RATIONALE FOR STUDY DESIGN

The study was designed to allow us to both: 1) identify the effect of income instability on mental health. For this, it is crucial to hold average income constant when varying income instability. And 2) decompose the effects of predictable and unpredictable instability and compare them to the effect of increasing the level of income, we will compare the outcomes in the predictable and unpredictable arms to the stable income and control arms. Additionally, we will isolate the effect of *ex-ante* income uncertainty by comparing participants who have *ex-post* identical income realizations. Each of these analyses are explained in greater detail below.

Effect of Level. We will estimate this effect by comparing the Control and Stable Income arms. The study earnings of both of these arms will be stable over time.

Effect of Predictable Instability. We will estimate this effect by comparing the Stable Income and Predictable Instability arms. While the two arms will earn on average the same, the earnings of the Predictable Instability arm will vary over time while those of the Stable Income arm will not.

Effect of Unpredictable Instability. We will estimate this effect by comparing the Predictable Instability and Unpredictable Instability arms. While the Predictable Instability arm has a known average, the Unpredictable Instability arm will earn the same amount *in expectation*. The difference between them is that a Predictable Instability participant can anticipate the swings in her future income while the incomes of Unpredictable Instability participants are unpredictable. As discussed before, this difference between the two arms has two consequences. One is the *exante* income uncertainty, i.e., the Predictable Instability participant knows what to expect while the Unpredictable Instability does not. The other is that an Unpredictable Instability participant may have an income realization which is different from what she initially expected.

We explain next how our design permits separately estimating these two distinct consequences of unpredictable instability.

Effect of Ex-Ante Income Uncertainty. We will estimate *ex-ante* income uncertainty by comparing Unpredictable Instability and Predictable Instability participants with *identical earnings profiles over time.* E.g., we will compare the Unpredictable Instability participants to the Predictable Instability participants. They had identical profiles over the first 4 periods. But, the Predictable Instability participant knew these income swings in advance while the Unpredictable Instability participant did not. The comparison is internally valid because the earnings profile for the Unpredictable Instability participant is randomly determined. To compensate for using a subsample of the arm, more individuals will be assigned to it.

Effect of Income	Table 4: Group Comparisons and the Effects They Estimate			
estimate the effect of	Comparison of	Estimates Effect of		
income realizations	Stable Income to Control	Level of Income		
(what actually happened) by	Predictable Instability to Stable Income	Predictable Instability		
comparing	Unpredictable Instability to Predictable Instability	Unpredictable Instability		
Unpredictable Instability	Unpredictable Instability and Predictable Instability with Identical Earnings Profiles over Time	Ex-Ante Income Uncertainty		
participants who by chance end up with	Unpredictable Instability w/ Diff. Income Realizations	Ex-Post Income Realizations		

different income realizations.

Justification of the Control: For our study we will randomly select individuals from those determined to be eligible to serve as an internal control group for comparison as there may be significant time trends in this population given the progression through the lean season. These individuals will be surveyed following the same timeline as all other participants, but not participate in the work program. Given that our sample density is less than five percent in any selected village, we do not anticipate spillovers from randomly sampled individuals in treatment arms to or from individuals in the control arm.

